9.5. Interim Analyses and Stopping Rules

There are no plans to conduct any interim analyses of primary and secondary outcome data prior to study completion. Manuscript and abstract presentations will focus on methodological and descriptive aspects of the study. No final data and safety monitoring plan has been discussed in detail and approved by NCCIH. In the event that such a plan involves a DSMB we propose an adverse event listing report rather than an interim analysis.

Similarly, we do not plan to conduct any futility analyses prior to termination of the study. As this is not a treatment study, but a brief 2-session based mechanistic study futility in the sense of lack of symptomatic improvement of CTS does not carry the same implications because the study consists of 2 visits which are aimed to measure an immediate nerve-specific, local physiologic response, whereas a treatment protocol for CTS typically involves 2 sessions per week over a period of 6-8 weeks and needling of additional acupuncture points than the ones tested in this study.

10. DATA COLLECTION AND QUALITY ASSURANCE

10.1. Data Collection Forms and Participant Confidentiality

The research material obtained from all subjects consists of relevant medical history information as part of the screening process, physiologic data such as nerve conduction parameters and sensory threshold values. No research personnel will have access to individually identifiable private information about human subject. Privacy and anonymity will be assured by replacing names and other identifying information with encoded identifiers, with the encoding key kept in a separate secure location. The PI will fill out the Study Screening Form (Appendix A) during screening in the EMG lab or in Neuromuscular clinic. For subject confidentiality, from the time of screening, only a 5-letter name code will be used to identify the subject. No study forms (beside the consent form) will contain a subject's name. A key to 5-letter codes and subject identities will be kept in a password protected document on OHSU's database, which requires network and workstation login. All methods to maintain subject confidentiality will adhere to HIPAA standards. HIPAA Authorization is part of the study consenting process.

All stored electronic data will be kept in password-protected documents, on computers protected by OHSU network password. Paper data will be stored in a locked secure cabinet, away from public access. Data storage will be compliant with all HIPAA and OHSU IRB regulations. All research materials will be used for research purposes only.

Experimental data from Week 1 and Week 2 will be recorded by a blinded investigator – [name], using the study Data Form (Appendix A). As [name] will be blinded to the intervention, the acupuncture data – acupuncture points used and modality (MA, LF-EA or HF-EA) will be filled out by the acupuncturist at the end of the study session.

10.2. Data Management

This is a small pilot mechanistic study involving a sample size of 60 subjects. We will not be needing a data management organization or coordinating center. Data entry will be performed by [name] or a trained volunteer, who will not be involved in outcome measure assessment in any other way. They will use the data recorded in the *Data Form* (Appendix A). Data will be stored in a password-protected Excel spreadsheet. Once a subject completes the study, the PI will verify that the Data Form contents are entered correctly as PI will bear ultimate responsibility for data. This Excel spreadsheet be used by the statistician [name], MS to conduct study data analysis as outlined above.

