3.4. Blinding

As this is a mechanistic study comparing acupuncture to acupuncture intervention, it is impossible to blind subjects in the conventional sense. Depending on a subject's knowledge of anatomy and acupuncture, however, a subject may or may not be aware as to which nerve is targeted for intervention on each week.

All QST assessments will be performed in blinded fashion and the investigators assessing the outcome measures will not be delivering the intervention (acupuncture). QST assessments will be performed by a blinded investigator ([name]), who will be seated behind a screen with the subject's arm, needles and QST probes not visible. The PI will not be involved in QST measurements. Additionally, the PI will be blinded to the acupuncture intervention, which will be delivered by a licensed acupuncturist ([name] or [name]).

Week 1 QST and NCS baseline will be assessed in non-blinded fashion, prior to randomization. Following these initial measurements, the PI will screen the subject for Secondary Exclusion criteria. Once the subject is determined eligible, the PI will leave the room. PI will be blinded to randomization (MA, LF-EA or HF-EA) and treatment assignment (median or ulnar nerve). Randomization will be performed by the study acupuncturist and the other investigators will be blinded to it.

The PI will return to the room once the acupuncture intervention has been completed, the post-acupuncture QST measurements obtained and acupuncture needles removed, in order to perform the post-acupuncture NCS and remain blinded to the intervention.

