4.3. Study Enrollment Procedures

Potential participants will be identified through screening OHSU's EMG lab and neuromuscular clinic patient schedules. Basic eligibility screening will be conducted using OHSU's electronic medical record database (EPIC). Patients, who pass this medical record screening will be approached by the PI. If a patient is interested, the PI will explain the objectives, risks and benefits of the study. At this point if a patient agrees to screening, the PI will proceed with an evaluation based on medical history, habits and recent (within last 2 years) EMG/NCS. The screening results will be documented using the *Subject Screening Form* (Appendix A). If a potential subject is determined to be eligible, the PI will answer all his/her questions, inform the subject that he/she may withdraw consent at any point and obtain informed consent for the study. This will involve presenting the subject with a *Lay Language Protocol Summary* and an *OHSU Consent-and-Authorization form* (as required by OHSU IRB) is also included in Appendix A.

Following enrollment, subjects will come to the lab for initial screening, consisting of QST and NCS. Following this testing, if they pass the Secondary Exclusion Criteria, subjects will be randomized to MA, LF-EA and HF-EA, using a computer-generated stratified randomization based on age and gender.

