4.4. Stratified Randomization

Subjects will be randomized to the 3 intervention groups, using a specially-designed computer program which will enable stratified randomization based on 2x2 categories where one category is gender (M/F) and the other is projected median age split of 56, based on age of enrolled pilots and clinic patients with carpal tunnel syndrome (18-56/57-75).

Gender and age have confounding effect on proper estimation of NCS and QST as they vary by age and sex. Specifically, men tend to have faster nerve conduction velocities (NCV) and larger nerves than women and with age NCV declines and sensory thresholds, measured by QST tend to rise (38, 49, 55, 56). Randomization will be performed by study acupuncturist, and all outcome assessors will be blinded to it.

The randomization program is also designed to offer random order of acupuncture intervention location (median vs ulnar nerves), with a built-in ability to assign 50% of subjects within a group to median nerve first and the other 50% - to ulnar nerve first.

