5.2. Experimental Procedure Timeline (Figure 1)

During Week 1, enrolled and consented subjects will come to the lab for Week 1 Baseline QST and NCS testing as outlined above. During this baseline testing subjects will be introduced to the QST equipment and will undergo assessment of baseline cold detection threshold (CDT) and vibration detection threshold (VDT), as well as baseline NCS as outlined above. This would take approximately 1.5 hours and both procedures are non-invasive.

Following assessment of Baseline QST and NCS, subjects will be screened for Secondary Exclusion criteria, which relate to their CTS diagnosis and ability to tolerate NCS and QST (**Figure 1**). Subjects who do not pass the Secondary Exclusion Criteria will exit the study, with proper documentation of why they were ineligible.

Those who pass the Secondary Exclusion Criteria will be randomized to MA, LF-EA and HF-EA, as well as undergo random treatment assignment of median (PC3, PC5) or ulnar (HT3, HT4) nerve. Following randomization a subject will undergo acupuncture for 20 minutes involving 2 needles as outlined in detail above.

Following acupuncture, Week 1 Post-acupuncture QST (CDT and VDT) and NCS will be obtained in a manner analogous to the Week 1 Baseline QST and NCS testing outlined above. QST will be obtained first, with the needles retained in position, followed by needle removal and conduction of NCS. This will conclude Week 1. Total estimated time of Week 1 procedures is 4-4.5 hours. Subjects will be provided with water, bathroom break/other breaks as needed and a healthy snack.

Week 2 procedures will occur exactly one week after Week 1, as close to the same time of day as possible. Week 2 will start with Week 2 Baseline QST and NCS testing, following the same methodology as the Week 1 Baseline QST and NCS outlined above, although subjects will not be screened for inclusion/exclusion criteria at Week 2. A second baseline is necessary because in our experience even a single intervention to PC3, PC5 or HT3, HT4 may alter NCS and QST parameters of the median and ulnar nerves, respectively.

Once Week 2 Baseline QST and NCS testing is obtained, acupuncture will be delivered to the nerve not treated during Week 1. For example, if a given subject is randomized to LF-EA and randomly assigned to ulnar nerve acupuncture in Week 1, the same subject will be administered LF-EA to the median nerve in Week 2, following Week 2 Baseline QST and NCS (Figure 1).

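### Section 10.2 has the PI, who decides final eligibility and performs the post-acupuncture NCS, check Data Forms that reveal past allocations, so later assignments can be guessed better than chance despite the blinding stated in sections 3.4 and 4.4

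*Combined protocol and SAP*

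**What the plan says.** Section 3.4 (Blinding) states the protection: "PI will be blinded to randomization (MA, LF-EA or HF-EA) and treatment assignment (median or ulnar nerve"). The PI leaves before randomization and returns after needle removal "in order to perform the post-acupuncture NCS and remain blinded to the intervention". Section 4.4 extends blinding to the randomization to every outcome assessor.

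The same person controls entry. In section 4.3, "Patients, who pass this medical record screening will be approached by the PI", and in section 3.4, after the Week 1 baseline tests, "the PI will screen the subject for Secondary Exclusion criteria". Randomization follows directly.

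Section 10.1 has a blinded investigator record the measurements. Points used and modality "will be filled out by the acupuncturist at the end of the study session", because that recorder is blinded. In Appendix A these fields sit on the Data Form, between the baseline and post-acupuncture readings.

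Section 10.2 then says: "Once a subject completes the study, the PI will verify that the Data Form contents are entered correctly". It mentions no masked copy and excludes no field.

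Allocation is to three groups of 20 (Précis). Section 4.4 stratifies by gender and age and describes a program "with a built-in ability to assign 50% of subjects within a group to median nerve first and the other 50% - to ulnar nerve first". No block size or other balancing method is given.

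**The concern.** Points and modality are the two facts that section 3.4 withholds from the PI. Needling at PC3 and PC5 means the median nerve was treated; HT3 and HT4 mean the ulnar. A PI who follows section 10.2 sees both for each completed subject and builds up a list of past allocations. When group sizes and nerve order are being balanced, that list carries information about the next assignment.

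This matters because subjects cannot be blinded in the usual sense, as section 3.4 acknowledges, so assessor blinding is the main safeguard. An NCS assessor with a belief about which nerve was needled, or by which modality, may without intent place cursors or repeat stimulations in line with it. That bears on the treated-versus-untreated and median-versus-ulnar contrasts (Aims 1 and 2) and the modality ranking (Aim 3). An anticipated modality could also colour a borderline eligibility decision, which bears on Aim 3.

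**Working it through.** The plan gives no figure to reproduce here. The check has two parts: whether the sections conflict, and how much past allocations reveal.

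**1. The sections side by side.** Section 3.4: the PI must not know modality or nerve. Section 10.1 and Appendix A: both are on the Data Form. Section 10.2: the PI checks the contents of that form for each completed subject. A PI who follows 10.2 as written learns what 3.4 withholds, for every completed subject.

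**2. Timing.** Section 4.5 expects 2-4 subjects per month, one every 30/4 = 7.5 to 30/2 = 15 days. Section 7.2 gives an 8-day study period. So when a new subject is randomized, usually at most the latest one is incomplete, and earlier forms can already have been verified.

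**3. Predictability.** There are 3 modalities × 2 nerve orders = 6 cells; 20 per modality at 50:50 gives 20 × 0.5 = 10 per cell. The scheme is not stated, so three were assumed. Each was simulated over 2,000 trials of 60 subjects. The guesser knows the balancing rule, the current stratum and all past assignments, and picks the likeliest remaining option. The block schemes use four equally likely strata.

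| Assumed scheme | Order guessed | Modality guessed | Order certain |
|---|---|---|---|
| Exact 10 per cell, one list | 57.2% | 42.4% | 1.91/60 = 3% |
| Blocks of 12 within strata | 62.0% | 48.1% | 6.16/60 = 10% |
| Blocks of 6 within strata | 66.7% | 53.9% | 12.89/60 = 21% |
| PI kept blind (chance) | 50% | 33.3% | 0% |

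If the latest subject's form has not yet been seen, order falls to 56.4%, 61.1% and 64.7%, and modality to 41.3%, 47.0% and 51.3%.

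**4. Closed-form check of the order column.** For a complete list of 2n with n of each order, the best guesser expects n + 2^(2n−1)/C(2n,n) − 1/2 correct.
- n = 30: (30 + 4.874 − 0.5)/60 = 57.3%, against 57.2% simulated.
- n = 6: (6 + 2048/924 − 0.5)/12 = 64.3%, against 62.0%.
- n = 3: (3 + 32/20 − 0.5)/6 = 68.3%, against 66.7%.

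The simulated block figures are slightly lower because each stratum usually ends part-way through a block, and early positions in a block are the hardest to guess.

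**5. Reach.** One guess of order covers both visits, because in Week 2 "acupuncture will be delivered to the nerve not treated during Week 1". The PI takes no part in QST under section 3.4, so cold and vibration thresholds do not pass through this route.

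**The case against.** The case on the other side is substantial.

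- **The verified subject is not unblinded.** The check comes after completion, when that subject's NCS is done. This stands; any harm falls on later subjects.
- **The percentages are illustrative.** Section 4.4 describes an ability to assign 50%, section 9.1 treats 20 per arm as a goal for completers, and nothing gives the PI the balancing rule. A PI relying on memory would guess less well. Simple randomization would make past allocations uninformative, although it would not deliver the balance described. This stands, and the figures should be read as what an optimal guesser could do.
- **Eligibility leaves limited room for judgement.** Section 5.1.1 sets explicit rules for failed QST, hypoalgesia and hyperalgesia, and section 4.2 gives numerical criteria for severe disease. This largely stands, so the eligibility route is the lesser one.
- **The study is an exploratory pilot.** True, but the plan still promises a blinded assessor.

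A reader might infer three stronger things that the documents do not support. First, that assessors are unblinded in Week 2 by the Week 1 form: no section has an assessor reopen it, and the form header suggests a separate form per visit. Second, that selective admission could create the nerve-specific effect of Aims 1 and 2: every randomized subject is scheduled for treatment of both nerves, so foreseeing the order changes only which comes first. Third, that the guess rates convert to a stated bias: this needs the amount by which belief shifts an NCS reading, and the documents give no value for it.

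None of this removes the conflict between section 10.2 and sections 3.4 and 4.4.

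**Conclusion.** The concern holds in a limited form. The data-verification rule does not preserve the PI blinding the plan states: it gives the person who makes the final eligibility decision and performs the post-acupuncture NCS a growing record of past allocations. Under the assumed balanced schemes, full use of that record raises correct guesses of nerve order to 57-67% and of modality to 42-54%, with order certain for about 3-21% of subjects. These figures rest on an unstated balancing method and on a PI who knows the rule and every past assignment.

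The outcomes exposed are the NCS measures in all three aims, through assessor expectation, and to a lesser extent the Aim 3 comparison, through eligibility. CDT and VDT are not affected by this route. Whether any bias would be large enough to matter in NCS units cannot be determined from the documents. The case for acting rests on restoring a stated safeguard at almost no cost, not on a demonstrated distortion of results.

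**What to change.** Move the acupuncture block (points and modality) off the Data Form to a separate sheet identified by subject code, kept by the acupuncturist and passed only to the data-entry person or the statistician. For this to work, those entries must also stay out of the spreadsheet that the PI opens for checking.

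Amend section 10.2 so that during the trial the PI verifies only the QST and NCS entries. The acupuncture entries are verified by the data-entry person or statistician, or by the PI after the last Week 2 measurement and database lock.

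As a precaution, state that the sheet is also withheld from the PI and the QST assessor between Week 1 and Week 2, since the Week 1 nerve fixes the Week 2 nerve.

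With the PI masked, guessing returns to 50% for order and 33.3% for modality whatever the balancing method, so the randomization blocks need no change. The cost is one split form page and a reworded passage in section 10.2, with no extra subjects, visits or staff. The one drawback is that the PI does not personally check the acupuncture entries until the end.

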10.3. Quality Assurance and Training

All study staff are trained in Protection of Human Subjects, Responsible Conduct of Research and Conflict of Interest as mandated by OHSU’s IRB. Staff will be familiar with this study protocol and trained in study procedures in lab practice sessions.

Over the past 1.5 years we have achieved lab consistency and reproducibility and have successfully performed the protocol on 3 pilot subjects. [name] has undergone training in NCS and QST under the direction of [name], MD, PhD, who was director of the EMG lab during [name] fellowship.

10.4. Protocol Deviations

Protocol deviations will be reported to [name] and recorded. When appropriate, these will be reported to OHSU’s IRB and included in DSMP.

10.5. Monitoring

Study monitoring will be performed by NCCIH, who will have access to all study records upon request.

11. PARTICIPANT RIGHTS AND CONFIDENTIALITY

Subjects can withdraw consent from the study at any point, as outlined in the *OHSU Consent-and-Authorization Form* (Appendix A).

11.1. Institutional Review Board (IRB) Review

This study will be overseen by OHSU’s IRB and run in concordance with all IRB regulations and procedures including but not limited to informed consent, HIPAA release authorization,

protection of human subject, responsible conduct of research, conflict of interest and adverse event documentation, reporting and monitoring.

11.2. Informed Consent Forms – see Appendix A and section 4.3

11.3. Inclusion of Women and minorities

Both genders and all ethnicities are included in the study. All minorities are included in our recruitment pools. We anticipate that the ethnic distribution of the study will reflect that of OHSU's clinic population, which is a reflection of the population of Oregon and Southern Washington. So far 2 out of our 3 pilot subjects have been women and 1 of the 3 was Hispanic.

Children will be excluded from the study as Carpal Tunnel Syndrome is exceedingly rare in the pediatric population and children under a certain age cannot sustain attention and focus to be reliable QST reporters.

Patients without English proficiency will also be excluded from the study as QST reporting is a timed test, thus making translation impossible.

11.4. Participant Confidentiality – see 10.1

11.5. Study Discontinuation

This study may be discontinued at any time by the IRB, the NCCIH, the OHRP, the FDA, or other government agencies as part of their duties to ensure that research participants are protected.

12. PUBLICATION OF RESEARCH FINDINGS

Any presentation, abstract, or manuscript generated from this study will be made available for review by NCCIH prior to submission. Additionally, NCCAM and [name] K23 grant will be acknowledged in all publications.

 Severe neuropathy symptoms – unable to tolerate acupuncture or QST
 CTS release surgery
 Other surgery on the arm or shoulder
 Change in opioid, benzodiazepines, SSRIs or other sedating medications in the past 2 months

SUBJECT SCREENING FORM

Please list your current medications and the doses (if you know them):

EXCLUSION CRITERIA

Check if you have any of the following medical problems/conditions:

- Wrist or elbow fracture, past arm trauma, loss of fingers, scarring
- Alzheimer's disease or other Mental Disability
- Epilepsy
- Other condition affecting sensation such as past stroke, Multiple Sclerosis or spinal cord disorder (Please specify) _____
- Cardiac Pacemaker
- Hospitalization for anxiety or depression in the past 3 months
- Other psychiatric condition you are being treated for (Please specify)

- Bleeding/Clotting condition
- Pregnancy

- Arthritis affecting the hands and fingers
- Thyroid problems
- Past chemotherapy treatment
- Use of any experimental medications within the **past 6 months**
- Any skin condition in the arm (dermatitis, bruises, weeping skin, skin lesions, infected skin, or necrotic skin)

- Have you had a change in your medications in the **past 2 months?**
 - Yes** – Please list specify below
 - No** (skip to next question)

- Have you used any illicit drugs, including marijuana **in the past month**
(Response will be strictly confidential) Yes No

- List how many (if any) drinks of alcohol you consume per week. List “0” if less than 1 per week.
_____ (Number) of drinks per week

SUBJECT 5- LETTER CODE _____ DATE _____

___ WEEK 1 ___ WEEK 2

Local Effects of Acupuncture on the Median and Ulnar Nerves
DATA FORM

BASELINE Temperature _____

COLD Detection Threshold

MEDIAN

ULNAR

#1 _____

#1 _____

#2 _____

#2 _____

#3 _____

#3 _____

Average _____

Average _____

VIBRATION Detection Threshold Temperature _____

MEDIAN

ULNAR

#1 _____

#1 _____

#2 _____

#2 _____

#3 _____

#3 _____

Average _____

Average _____

NERVE CONDUCTION STUDIES Temperature _____

MEDIAN Motor

Supramax CMAP Amplitude WRIST _____ ELBOW _____

CMAP Area WRIST _____ ELBOW _____

NCV _____

Distal Motor Latency WRIST _____ ELBOW _____

Duration (Wrist) _____ (Elbow) _____

ULNAR Motor

Supramax CMAP Amplitude WRIST _____ ELBOW _____

CMAP Area WRIST _____ ELBOW _____

NCV _____

Distal Motor Latency WRIST _____ ELBOW _____

SUBJECT 5- LETTER CODE _____ DATE _____

___ WEEK 1 ___ WEEK 2
Duration (Wrist) _____ (Elbow) _____

MEDIAN Sensory 2nd Digit Temperature _____
Supramax SNAP Amplitude _____
SNAP Area _____
NCV Wrist _____
Distal Sensory Latency 1) _____ 2) _____

ULNAR Sensory 5th Digit
Supramax SNAP Amplitude _____
SNAP Area _____
NCV Wrist _____
Distal Sensory Latency 1) _____ 2) _____

ACUPUNCTURE SETTING START TIME _____ Temperature _____
ACUPUNCTURE POINTS _____
___ Manual
___ Low-frequency
___ High-frequency

POST-ACUPUNCTURE MEASUREMENTS Temperature _____

COLD Detection Threshold

MEDIAN	ULNAR
#1 _____	#1 _____
#2 _____	#2 _____
#3 _____	#3 _____
Average _____	Average _____

VIBRATION Detection Threshold Temperature _____

MEDIAN	ULNAR
#1 _____	#1 _____
#2 _____	#2 _____
#3 _____	#3 _____
Average _____	Average _____

SUBJECT 5- LETTER CODE _____ DATE _____

___ WEEK 1 ___ WEEK 2

NERVE CONDUCTION STUDIES

Temperature _____

MEDIAN Motor

Supramax CMAP Amplitude WRIST _____ ELBOW _____

CMAP Area WRIST _____ ELBOW _____

NCV _____

Distal Motor Latency WRIST _____ ELBOW _____

Duration (Wrist) _____ (Elbow) _____

ULNAR Motor

Supramax CMAP Amplitude WRIST _____ ELBOW _____

CMAP Area WRIST _____ ELBOW _____

NCV _____

Distal Motor Latency WRIST _____ ELBOW _____

Duration (Wrist) _____ (Elbow) _____

Median Sensory 2nd Digit

Temperature _____

Supramax SNAP Amplitude _____

SNAP Area _____

NCV Wrist _____

Distal Sensory Latency 1) _____ 2) _____

Ulnar Sensory 5th Digit

Supramax SNAP Amplitude _____

SNAP Area _____

NCV Wrist _____

Distal Sensory Latency 1) _____ 2) _____
